6.1 General Considerations

Unless otherwise specified, the following general principles apply to the planned statistical analyses. All statistical analysis will be conducted using SAS version 9.4 or later (SAS Institute Inc., Cary, NC) or other widely-accepted statistical or graphical software as required.

6.1.1 Descriptive Statistics

Continuous data will be summarized with mean, standard deviation, median, minimum, maximum, and number of evaluable observations. Categorical variables will be summarized with frequency counts and percentages. Confidence intervals may be presented, where appropriate.

Statistical Analysis Plan		Page 14 of 23
Sponsor Luminopia	Study Luminopia One Amblyopia Vision Improvement Study	

6.1.2 Study Day

Study day 0 is the date of the randomization. For each participant, duration in study will be based on date of randomization and the last study contact date which is the latest date of all follow-up visits, assessments, adverse event onset or resolution, and study exit including date of death.

6.1.3 Visit Windows

The primary endpoint analyses on mean change in BCVA (in both amblyopic and fellow eyes) will be based on in-window visits only. An additional sensitivity analysis will be conducted using all available data associated with the 12-week visit regardless of in or out of window. Unless otherwise specified, all secondary and exploratory visit-based assessments will be analyzed for each analysis time point according to the nominal visit entered in the Case Report Form (CRF) regardless of if it is out of window. See section 3.4 in the protocol for visit window specifications.

6.1.4 Statistical Significance

The primary efficacy and safety endpoints will be performed using one-sided tests and a 0.05 significance level. Any additional exploratory hypothesis testing will be performed at the two-sided 0.05 significance level. P-values will be rounded to three decimal places. If a p-value is less than 0.001 it will be reported as "<0.001". If a p-value is greater than 0.999, it will be reported as ">0.999".

6.2 Analysis Populations

The following analysis populations are defined for analysis:

- 1. Intention-to-treat (ITT) Analysis Set:** The intention-to-treat (ITT) population consists of all enrolled participants who were subsequently randomized. The ITT set will be analyzed according to randomized treatment assignment regardless of treatment actually received. The ITT population will not include participants who did not meet eligibility criteria at the time of enrollment and are ultimately deemed ineligible for the study, including participants who are withdrawn from the study due to insufficient internet.
- 2. As-Treated Analysis Set:** The as-treated (AT) population consists of participants enrolled and randomized, however treatment group assignment for the purposes of analysis will be based on the actual treatment received. Participants randomized to the Luminopia One group with ≤ 25% adherence in device use at 12 weeks will be analyzed as control participants.
- 3. Per-Protocol Analysis Set:** The per-protocol (PP) population consists of all ITT participants who were treated according to randomized assignment, who had adherence > 25% in Luminopia One Use for the therapeutic group, and who had no major protocol deviations that could affect the endpoints of interest. Protocol deviations will be reviewed and defined as major prior to analysis

Statistical Analysis Plan		Page 15 of 23
Sponsor Luminopia	Study Luminopia One Amblyopia Vision Improvement Study	

of study outcomes. The 25% adherence threshold for the PP population was determined from pilot trials on Luminopia One, in which all enrolled participants with > 25% adherence and no major protocol deviations showed improvements from using the therapeutic. Adherence will be captured while maintaining masking of the study in accordance with the Masking Plan.

The ITT population will be used for analysis and interpretation of the primary and secondary efficacy endpoints and the co-primary safety endpoint assessing BCVA in the fellow eye. Supportive analysis for the primary and secondary efficacy endpoints will be performed using the PP population to provide insight into the potential impact of protocol deviations on the primary results of the study. The AT cohort will be used to characterize and assess safety, including the co-primary safety endpoint evaluating frequency and severity of all related Adverse Events, as well as supportive efficacy analyses.

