6.6.2 Primary Safety Endpoint

The co-primary analysis of safety will test if the mean change in fellow eye visual acuity of the therapeutic group from baseline to 12 weeks is non-inferior to the mean change in fellow eye visual acuity of control group within a margin of 0.10 logMAR. The formal hypothesis being tested are:

$$H_0: \mu_{\text{therapeutic}} - \mu_{\text{control}} \geq \delta$$

Statistical Analysis Plan		Page 18 of 23
Sponsor Luminopia	Study Luminopia One Amblyopia Vision Improvement Study	

$$H_a: \mu_{\text{therapeutic}} - \mu_{\text{control}} < \delta$$

where μ is the change from baseline (follow-up - baseline) for both the control and therapeutic participants and δ is the non-inferiority window of 0.10 logMAR. The statistical test is a two-sample one-sided T-test which will be done at the 0.05 level of significance. An upper 95% confidence limit for the difference will also be presented. The endpoint will be considered met if the p-value is < 0.05 .

The endpoint will be evaluated using the ITT population with no imputation for missing data. Assessments from out of window visits will be considered missing in the primary analysis. Supplementary analysis will be provided based on ITT with imputation, PP and AT cohorts, as described in the primary efficacy endpoint analysis.

In addition to the formal test on the mean change in fellow eye visual acuity, the primary safety endpoint will report the frequency and severity of all related Adverse Events (anticipated and unanticipated). Count of events, percent of participants who experienced an event, and an exact 95% confidence interval of the event rates will be presented for each treatment group by event type. No formal hypothesis testing will be performed. Event rates will be summarized for clinical interpretation. Safety analyses on Adverse Events will be based on the AT analysis cohort.

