6.6.5 Secondary Safety Endpoints

Safety analyses will be performed on the AT population. Results from any hypothesis testing will be considered exploratory and no adjustments for multiple testing will be made.

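### The as-treated set used for adverse events counts device-arm children at or below 25% adherence as controls, so events in children who used the device are reported under control

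*SAP*

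**What the plan says.** SAP section 6.2 gives the AT principle: "treatment group assignment for the purposes of analysis will be based on the actual treatment received". The next sentence gives the rule: "Participants randomized to the Luminopia One group with ≤ 25% adherence in device use at 12 weeks will be analyzed as control participants".

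The same section explains the cut-off, but for another set: "The 25% adherence threshold for the PP population was determined from pilot trials on Luminopia One". The reason offered is that pilot participants above that level, without major deviations, improved.

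Three places make AT the safety population:
- Section 6.2: "The AT cohort will be used to characterize and assess safety, including the co-primary safety endpoint evaluating frequency and severity of all related Adverse Events".
- Section 6.6.2: "Safety analyses on Adverse Events will be based on the AT analysis cohort".
- Section 6.6.5: "Safety analyses will be performed on the AT population".

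Section 6.6.2 plans event counts, the percentage of participants affected, and "an exact 95% confidence interval of the event rates will be presented for each treatment group by event type". The groups in that table are therefore the AT groups. The fellow-eye acuity test in the same section is primary on ITT, with AT only supplementary.

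**The concern.** For any device-arm child above zero and up to 25% adherence, the rule departs from the principle stated just before it. The child used Luminopia One, yet the child's events count against refractive correction alone. A cut-off chosen because children above it improved says nothing about how much use is needed to cause harm.

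Adherence is also a post-randomisation variable that harm can change. A child who stops because of an event accumulates less use and so is more likely to be moved, taking the event along. The AE component has no formal test, so the by-group table is itself the AE evidence, both at the interim and at the end. If its grouping is wrong, the readers who are to interpret it clinically are shown the wrong contrast.

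**Working it through.** **1. Is attribution restored elsewhere in the SAP?**
- Section 3.4.1 summarises events over all participants, not by arm.
- Section 6.4 reports the number in each analysis population and reasons for exclusion, not events.
- Section 6.6.5.1 tabulates AEs in the manner of the primary safety analysis. Further summaries are optional.

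No planned table groups events by randomised arm or by any device use.

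**2. Inputs.** From the SAP: 1:1 allocation and 140 enrolled, so 70 per arm. The SAP states no AE risk and no expected share of low adherers, so there is no planned figure to reproduce. Everything below is assumed for illustration, and all low adherers are taken to have had some use.

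Let L be the share of the device arm at or below 25% adherence, and let r_L, r_H and r_C be the AE risks in low adherers, other device users and controls. Arm size cancels under 1:1 allocation.
- Difference by randomised arm: L·r_L + (1 − L)·r_H − r_C
- Difference under AT: r_H − (r_C + L·r_L)/(1 + L)

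**3. Worked case.** L = 0.15, r_H = 0.10, r_C = 0.02, r_L = 0.30.
- Randomised: 0.045 + 0.085 − 0.02 = 0.110. The device rate is 13.0%, control 2.0%.
- AT: 0.10 − (0.02 + 0.045)/1.15 = 0.10 − 0.0565 = 0.0435. The device rate is 10.0%, control about 5.7%.

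**4. Varying the low-adherer risk** (L = 0.15, r_H = 0.10, r_C = 0.02; differences in percentage points)

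| r_L | Randomised | AT |
|---|---|---|
| 10% (equal risk) | 8.00 | 6.96 |
| 30% | 11.00 | 4.35 |
| 5% | 7.25 | 7.61 |
| 2% | 6.80 | 8.00 |

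**5. Varying the share of low adherers** (r_L = 0.30, other risks as above)

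| L | Randomised | AT |
|---|---|---|
| 10% | 10.00 | 5.45 |
| 20% | 12.00 | 3.33 |
| 30% | 14.00 | 1.54 |

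**6. Where the direction turns.** Setting the two differences equal gives r_L = [r_H(1 + L) + r_C]/(2 + L). At L = 0.15 this is (0.115 + 0.02)/2.15 = 6.28%. For L = 0.10, 0.20 and 0.30 it is 6.19%, 6.36% and 6.52%. Below that risk AT overstates the difference; above it AT understates it.

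**7. Higher base rates.** With r_H = 0.20, r_C = 0.05 and L = 0.15, equal risk gives 15.00 against 13.04, and r_L = 5% gives 12.75 against 15.00. Break-even is (0.23 + 0.05)/2.15 = 13.02%.

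**8. Early stopping of use.** The SAP does not define how adherence is calculated. If it is cumulative over 12 prescribed weeks, 25% corresponds to 0.25 × 12 = 3 weeks of full use. On that assumption, a child with full use who stops within about 3 weeks is moved to control together with the event. One who stops later stays in the device group.

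**The case against.** The strongest objection is about consequence. AEs have no hypothesis test and no pass criterion. Study success depends on the efficacy test and the fellow-eye test, both primary on ITT, so no error rate or success decision is at stake. That is correct, and it confines the point to the descriptive AE component. That component is nevertheless a named part of the primary safety endpoint, and a descriptive table must at least place events in the right group.

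The 25% sentence can also be read as the operational definition of treatment received rather than as a contradiction of it. Even on that reading, an efficacy-derived cut-off is unsuitable for attributing harm.

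The primary AE component covers related events only, so a device-related event listed under control might stand out as odd. A reader might notice it, but the percentages and intervals would still be wrong. In the broader AE tables, an unrelated illness or an event long after use ended is not clearly a device event. Children with no use at all were not exposed, and counting them as control misplaces nothing.

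Finally, size and direction are assumed, not established. At equal risk and 15% low adherers the shift is about one point, and it reverses when low adherers have clearly fewer events. The three-week scenario rests on a definition of adherence that the protocol may set differently. All of this stands, but the misplacement of exposed children's events does not depend on it.

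**Conclusion.** The concern holds. Followed as written, the SAP reports events in device-exposed children at or below 25% adherence under control, and no other planned table corrects this. The size cannot be derived from the SAP. At 15% low adherers with 10% and 2% base risks, the change runs from 8.0 to 7.0 points at equal risk and from 11.0 to 4.3 if harm drives low use. It reverses below a low-adherer risk of about 6.3%. These figures assume 1:1 arms and some use by every low adherer. The ITT fellow-eye test and the primary efficacy test are untouched. The by-group AE table should be corrected before any analysis, including the interim.

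**What to change.** In sections 6.2, 6.6.2 and 6.6.5, define a separate safety grouping for all AE analyses. Anyone who used Luminopia One at least once during the 12-week randomised period counts as therapeutic, and everyone else as control. Tabulating by randomised arm is an acceptable alternative. Keep the 25% rule only for supportive efficacy analyses.

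As a useful addition on which the point does not depend, list events in controls after they switch to the device in a separate table, so that they are neither charged to control nor lost.

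The cost is SAP wording and one population flag. The reported device AE rate may become less favourable.

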6.6.5.1 Adverse Events

AEs will be tabulated with the number of events and participants with event for each event type as described in the primary safety analysis. Additional summaries may be provided as necessary. Rates will be reported as the number of participants who experience at least one event during the analysis interval out of the total number of participants.

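### The As-Treated set used for adverse-event tables counts children with up to 25% device use as controls, so exposed children and their events appear under refractive correction

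*SAP*

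**What the plan says.** SAP 6.2 builds the As-Treated set on the treatment each child in fact received, then adds a threshold: "Participants randomized to the Luminopia One group with ≤ 25% adherence in device use at 12 weeks will be analyzed as control participants". It makes no exception for partial use or for safety analyses.

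The same section assigns this set to safety: "The AT cohort will be used to characterize and assess safety, including the co-primary safety endpoint evaluating frequency and severity". Section 6.6.2 repeats it: "Safety analyses on Adverse Events will be based on the AT analysis cohort". Section 6.6.5 says "Safety analyses will be performed on the AT population", and 6.6.5.1 carries the same layout forward: "AEs will be tabulated with the number of events and participants with event for each event type as described in the primary safety analysis". The display is by group: "an exact 95% confidence interval of the event rates will be presented for each treatment group by event type".

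The only rationale for the cut-off is in the Per-Protocol definition in 6.2: "The 25% adherence threshold for the PP population was determined from pilot trials on Luminopia One", because there "all enrolled participants with > 25% adherence and no major protocol deviations showed improvements from using the therapeutic".

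**The concern.** An as-treated safety table should show what happened to children who were exposed to the device. Under this rule, a child who used the device at 20% of the prescribed amount is listed as having had refractive correction only. That child leaves the device numerator and denominator and enters both for control.

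The threshold comes from an efficacy observation: pilot participants above it improved. That says nothing about how little use makes a child unexposed for harm. Adherence is also measured after randomisation and may itself depend on an adverse event. If an event makes a child cut back to 25% or less, the rule credits that event to refractive correction.

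The adverse-event report is a named part of the primary safety endpoint (3.2, 6.6.2), and the rates are offered for clinical interpretation. The by-group table is therefore what a reader would use to judge the device's tolerability.

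**Working it through.** **Step 1: the rule, section by section.**

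| Analysis | Set | Device children with >0% and ≤25% use appear as |
|---|---|---|
| Fellow-eye acuity, main analysis (6.2, 6.6.2) | ITT | Luminopia One |
| Related adverse events, primary safety endpoint (6.2, 6.6.2) | As-Treated | Control |
| Adverse events, secondary safety (6.6.5, 6.6.5.1) | As-Treated | Control |

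No adverse-event table by randomised arm or by any device use is specified in the text shown. Section 3.4.1 promises a summary over all participants, which does not separate the groups.

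**Step 2: who moves.** The SAP does not define the adherence measure behind the cut. If it is cumulative from baseline, as the wording of 3.3.4 suggests, a child reaches exactly 25% on stopping at week 0.25 × 12 / (use rate while using):
- 100% use: week 3.0
- 75% use: week 4.0
- 50% use: week 6.0

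Children who stop at or before that point move, as do persistent low users. The SAP does not say how a child who exits before 12 weeks is classified.

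**Step 3: effect on the by-group difference.** The SAP has no figure of its own to reproduce here. Let pD and pC be the event rates by actual device exposure, f the share of device children moved, and q their event rate. Arms are equal (1:1, Section 4), and all moved children are assumed to have had some use. Then

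As-Treated difference = (pD − f·q)/(1 − f) − (pC + f·q)/(1 + f).

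If q = pD, the first term is pD and the whole reduces to (pD − pC)/(1 + f). The multiplier is 1/1.05 = 0.95, 1/1.10 = 0.91 and 1/1.20 = 0.83 at f = 5%, 10% and 20%.

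**Step 4: illustration.** There are 140/2 = 70 children per arm. The event counts are assumptions: 14/70 device (20.0%, exact 95% interval 11.4 to 31.3) and 3/70 control (4.3%, 0.9 to 12.0), a difference of 15.7 points. With equal rates, this becomes 15.7/1.05 = 15.0, 15.7/1.10 = 14.3 and 15.7/1.20 = 13.1 points. In whole children:

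| Moved | With an event | Device column | Control column | Difference (points) |
|---|---|---|---|---|
| 7 (10%) | 0 | 14/63 = 22.2% | 3/77 = 3.9% | +18.3 |
| 7 | 1 | 13/63 = 20.6% | 4/77 = 5.2% | +15.4 |
| 7 | 4 | 10/63 = 15.9% | 7/77 = 9.1% | +6.8 |
| 7 | 6 | 8/63 = 12.7% | 9/77 = 11.7% | +1.0 |
| 7 | 7 | 7/63 = 11.1% | 10/77 = 13.0% | −1.9 |
| 14 (20%) | 0 | 14/56 = 25.0% | 3/84 = 3.6% | +21.4 |
| 14 | 3 | 11/56 = 19.6% | 6/84 = 7.1% | +12.5 |
| 14 | 7 | 7/56 = 12.5% | 10/84 = 11.9% | +0.6 |
| 14 | 8 | 6/56 = 10.7% | 11/84 = 13.1% | −2.4 |

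The large drops need moved children to have about four times the event rate of those who remain: 4/7 = 57% against 15.9% (ratio 3.6), or 7/14 = 50% against 12.5% (ratio 4.0). Under these inputs reversal needs 7 of 7 or 8 of 14.

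The difference widens when q < [pD(1 + f) + pC(1 − f)]/2. That is (0.220 + 0.039)/2 = 0.129 at f = 10% and (0.240 + 0.034)/2 = 0.137 at f = 20%, so slightly fewer events among low users is not enough.

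**The case against.** The case for leaving the rule alone has real substance. No event is lost: 3.4.1 summarises frequency over all participants, and 6.4 reports the size of each analysis population, which may help show how many children moved. The event rates carry no formal test, and the harm that is tested, fellow-eye acuity, is analysed by randomised arm on ITT. With equal rates, the attenuation is small beside the width of the interval for a rate such as 14/70. For a child with no device use, placement under control is a reasonable as-treated choice.

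All of this limits the consequence. None of it makes the classification right, because neither a pooled total nor a population count tells the reader which group's events came from children who had used the device.

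Several stronger readings are tempting but not supported:
- **That the table will conceal or reverse a device harm.** The SAP gives neither event rates nor adherence shares, reversal needs extreme inputs, and the difference can also widen.
- **That every early stopper moves.** This depends on an adherence measure the SAP does not define, and on how early exits are classified.
- **That the interim adverse-event report is affected.** Section 6.9.2 names no analysis set for it. Use of the As-Treated set there is an inference from the general rule.
- **That adverse events must be shown for all causes, mainly by randomised arm, or with a separate post-switch column.** These are reporting preferences beyond this defect.

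**Conclusion.** The point holds as a misclassification in the adverse-event tables. As written, device-exposed children with 25% adherence or less, and their events, are shown under refractive correction. The threshold behind this was chosen for efficacy and contradicts the principle on which the set is defined.

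The size cannot be settled from the SAP. The neutral case is a by-group difference multiplied by 0.95, 0.91 or 0.83 at 5%, 10% or 20% moved. This assumes equal arms, some use in every moved child, and the same event rate as in other device children. The difference shrinks further if events drove low use, and may widen if low users had clearly fewer events.

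The reach is limited to descriptive safety reporting. Study success, the sample size and the fellow-eye non-inferiority test do not depend on these counts. The wording should be corrected because the table belongs to the primary safety endpoint, but the point does not threaten the trial's formal conclusions.

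**What to change.** Give adverse events their own exposure rule in 6.2, and refer to it in 6.6.2 and 6.6.5. Suggested text:

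> For adverse-event analyses, every child randomised to Luminopia One who used the device at all is counted in the Luminopia One group. Only children with no device use are counted as control. The 25% adherence rule applies to supportive efficacy analyses only.

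This rule needs no 12-week adherence value, so it also settles children who leave early. The supplementary As-Treated analysis of fellow-eye acuity in 6.6.2 should state which definition it follows. A table by randomised arm may be added as a check.

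The cost is a few lines of SAP text. Device use is already recorded as adherence, and adverse events are already asked about at each visit and call (3.4.1). The downside is that children with very little exposure stay in the device denominator, which can lower the device rate if harm rises with use.

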6.3 Handling of Missing Data

Multiple imputation for missing data will be performed as a secondary approach with the ITT population, and results of the analysis with imputation of missing data will be considered supportive in nature and assessed for consistency with the primary analysis. Imputation will be based on regression methods using baseline covariates as independent predictors. If no significant predictors can be found, the following method will be used. Those participants completing the study will be categorized by age, sex, and treatment received. For a participant with missing data, the imputed value will be a random draw from those participants with data that have the same age, sex, and treatment. See Section 6.6 for imputation methods specific to the study endpoints.

In the case of partial dates (e.g. adverse event onset date), the unknown portion of the date of the event will be imputed. If the month and year are known, the 15th of the month will be used for analysis. If only the year is known, the event will be analyzed as if it occurred on June 30th of the known year. Imputation of partial dates is participant to the condition that it must occur on or after the randomization date. In the case where the imputed date is prior to the randomization date, the date of the randomization will be used.

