3.4 Safety Reporting

3.4.1 Adverse Events

The participant and parent(s) will be asked about anticipated and unanticipated adverse events at each visit and phone call. The frequency of known and unknown adverse events will be summarized for all participants.

4 Study Design

The proposed study is a multi-center randomized, controlled, masked, clinical trial which compares mean change in amblyopic eye BCVA from baseline with Luminopia One (“therapeutic”), to refractive correction (“control”). One-hundred and forty participants ($n = 140$) aged 4-7 years (inclusive) will be enrolled. Participants will be randomized 1:1 to the “therapeutic group”, to use Luminopia One, or the “control group”, to undergo continued refractive correction, for 12 weeks of treatment.

A group sequential design with a single interim analysis will be used to allow stopping for either early success or futility in both primary safety and efficacy endpoints. The interim analysis will be conducted after 75% of participants have completed their 12-week follow-up visit. The overall Type I error rate was set at 0.05.

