6.6.1.1 Primary Analysis

An analysis of variance will be performed to compare the change in VA from baseline to 12 weeks in the therapeutic and control groups. The primary objective will be assessed with the following hypothesis:

$$H_0: \beta_1 \geq 0$$

$$H_a: \beta_1 < 0$$

where β_1 is the coefficient from the following model:

$$Y = \beta_0 + \beta_1 * X_1,$$

where Y is the adjusted average change in BCVA in the amblyopic eye from baseline to 12 weeks, β_1 and X_1 are the coefficient and regression term for treatment arm (X_1 coded as therapy=1, control=0), respectively.

The hypothesis will be evaluated using a one-sided F-test for the coefficient associated with treatment group. A standard F-test will be used to determine if there is a significant difference in mean change from baseline between groups. The endpoint will be presented as average BCVA at baseline and 12 weeks, change in BCVA from baseline to 12 weeks in each treatment group, difference in BCVA change between treatment groups, two-sided 90% confidence interval of the difference, and p-value associated with the hypothesis test above. The endpoint will be considered met if the p-value for the coefficient is <0.05 .

The endpoint will be evaluated using the ITT population with no imputation for missing data.

Assessments from out of window visits will be considered missing in the primary analysis.

Supplementary analysis will be provided based on ITT with imputation, PP and AT cohorts.

The 24-week visit for participants in the control group who switch over to the therapeutic at the 12-week visit will not be a part of the primary analysis.

Statistical Analysis Plan		Page 17 of 23
Sponsor Luminopia	Study Luminopia One Amblyopia Vision Improvement Study	V

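### The partial-date rule in SAP 6.3 has a lower limit at randomization but no upper limit, so an imputed adverse-event onset can fall after the event's report, its resolution or study exit

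*SAP*

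**What the plan says.** Section 6.3 gives two fixed rules for a partial date and names adverse-event onset as its example. With only the day missing: "If the month and year are known, the 15th of the month will be used for analysis". With day and month missing: "If only the year is known, the event will be analyzed as if it occurred on June 30th of the known year". There is one correction: "In the case where the imputed date is prior to the randomization date, the date of the randomization will be used". No matching rule covers a date that comes out too late.

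Three other places bear on the result.

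- Section 6.1.2 bases duration in study on the last contact date, defined as "the latest date of all follow-up visits, assessments, adverse event onset or resolution, and study exit including date of death".
- Section 6.6.5.1 reports adverse-event rates as "the number of participants who experience at least one event during the analysis interval" out of all participants. The interval is not defined.
- Section 4 sets the randomized comparison at 12 weeks, and section 6.6.1.1 refers to "The 24-week visit for participants in the control group who switch over to the therapeutic at the 12-week visit". Some control children therefore have a second period, on the device.

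**The concern.** A mid-month or mid-year default is coarse against an 84-day randomized period. The SAP recognises that a default can give an impossible date, but corrects this on one side only. On the other side, an onset can be later than facts already on the case report form: the visit or call at which the event was reported, its resolution, or the child's exit.

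The direct consequences are impossible onset dates in the listings and an inflated duration in study. A possible further consequence concerns the safety summaries. Related adverse events are part of the primary safety endpoint, so it would matter if a wrong date removed an event from a date-limited table or moved it between the control and device periods of a child who switched.

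**Working it through.** The SAP states no figure for this rule, so there is none to reproduce. The check applies the rule to dates.

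**Inputs from the SAP.** Defaults of the 15th and 30 June, and the floor at randomization (6.3); 12 weeks = 84 days (4); switch at week 12 and a 24-week visit (6.6.1.1); last contact includes adverse-event onset (6.1.2).

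**Examples (non-leap year).**

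1. Year only. Randomized 7 January; 7 January + 84 days = 1 April, taken as exit. Imputed onset is 30 June. From 1 April to 30 June is 29 + 31 + 30 = 90 days, so duration becomes 84 + 90 = 174 days.
2. Month known. Randomized 10 January, week 12 on 4 April, event on 2 April recorded as April. Imputed onset is 15 April, 11 days after week 12.
3. Resolution. Onset recorded as April, resolution on 5 April. Imputed onset is 15 April, 10 days after resolution.
4. Switcher, dated too early. Randomized 1 August, switch on 24 October, event on 10 December known only by year. 30 June precedes randomization, so the date is reset to 1 August, in the control period.

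**How often a partial date lands after exit.** Assumptions not in the SAP: randomization uniform over a 365-day year, true onset uniform over days 0 to 84 (85 days), exit at day 84.

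- Month known: the problem arises when exit is on day d = 1 to 14 of a month, and then affects the d follow-up days in that month. Per year this is 12 × (1 + 2 + … + 14) = 12 × 105 = 1,260 event-days. 1,260 / (365 × 85) = 4.1%.
- Year only: for the 96 randomization dates from 1 January to 6 April, exit precedes 30 June and every event is dated after it. For the 84 dates from 9 October to 31 December, only events in the new year are affected: (1 + … + 84) / 85 = 3,570 / 85 = 42 full-date equivalents. (96 + 42) / 365 = 37.8%.
- For an early leaver at day 28 (29 days), the same steps give 1,260 / (365 × 29) = 11.9% and (152 + 14) / 365 = 45.5%.

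**Switchers** (switch at day 84, exit at day 168, all date combinations enumerated under the same assumptions):

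| Partial dates | Month known | Year only |
|---|---|---|
| Control-period event dated on or after the switch | 4.1% | 38.0% |
| Device-period event dated before the switch | 4.9% | 38.9% |
| Either error | 4.5% | 38.4% |
| Dated after the 24-week exit | 2.0% | 26.3% |

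A cap at study exit brings dates after exit to zero by construction. It leaves the share on the wrong side of the switch at 4.5% and 38.4%, because part of that error comes from dates that are too early (example 4), and dates that are too late can still fall before the 24-week exit. A separate rule is needed for switchers.

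All these percentages are shares of partial dates, not of all adverse events.

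**The case against.** The strongest reply is that no main result depends on onset date. Section 6.6.2 reports event counts, the percentage of participants affected and exact intervals by group and event type, with no date cut. The as-treated set in 6.2 assigns each child to one group, and no section divides a switcher's events at week 12. The rates in 6.6.5.1 use participants, not person-time, as denominator. Section 3.4.1 has families asked about events at every visit and phone call, so a date known only by year should be rare. All of this stands.

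It bars three stronger readings. A reader might infer that the rule removes events from the safety table; that follows only if the undefined analysis interval is read as ending at week 12 or exit. A reader might infer that it moves events between device and control; that follows only if switchers' events are split by period, which the SAP does not say. And a reader might note that exits on days 1 to 14 make up about 14 / 30.4 = 46% of calendar days and take this as the share of events misdated; it is the share of exit days on which misdating can occur, and the corresponding event share is the 4.1% above.

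It can also be said that 6.1.2 does not expressly count an imputed onset as a contact. But it does not exclude one either, and 6.3 says the imputed date is the one used for analysis. The plain reading carries the imputed date through.

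**Conclusion.** The point holds as a minor fault in a stated rule. With a floor and no ceiling, section 6.3 can give an onset later than the event's report, resolution or study exit, and section 6.1.2 then lengthens duration in study, by 90 days in the first example. These two effects need no further assumption beyond a partial date occurring.

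Omission from a date-limited summary, or placement in the wrong period for switchers, is conditional on choices that the SAP leaves open. Total adverse-event counts over all follow-up, the efficacy test and the fellow-eye test do not change. Under uniform dates and exit at day 84, about 4% of month-known and 38% of year-only partial dates fall after exit. The SAP gives no rate of partial dates; they are probably few, and year-only dates fewer still.

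**What to change.** Keep the 15th and 30 June defaults and the floor at randomization, and add three sentences.

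1. In 6.3: the imputed date may be no later than the earliest of the report date, the resolution date and the study exit date.
2. In 6.3: for a control participant who switches to the device, the imputed date stays within the treatment period in which the event was reported, where the known date parts allow it.
3. In 6.1.2: imputed dates are not used for the last study contact date.

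In the first example the onset then falls no later than 1 April and duration returns to 84 days. Replacing the mid-month default by the earliest possible date, or assigning every ambiguous switcher event to the device, would be a different convention and is not needed to correct this fault. The cost is a small amount of programming.
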